1.6.4 Clinical Experience with Ruxolitinib Dose Escalation in Normal Healthy Volunteers
As part of the initial clinical safety studies performed by commercial drug sponsor, patients and normal healthy volunteers (NHV) were treated with 50 mg twice daily, 100 mg once daily and in some cases individual doses of 200 mg ([Figure 9](#)).

A. Percent Inhibititon of STAT3 Phophorylation versus Serum concentration of Ruxolitinib

B. Serum Ruxolitinib Concentration with Augmented Dosing Regimens

[figure not shown]

Figure 9 A and B: Percent inhibition of phosphoSTAT3 versus log concentration of (INCB018424) Ruxolitinib and serum Ruxolitinib concentrations with augmented dosing regimens⁴⁸

Results from these NHV showed the more dose intense regimens achieved serum concentrations of ruxolitinib with greater potential to inhibit STAT3 phosphorylation without producing clinically significant AEs. In addition to monitoring for clinical toxicities, the sponsor also performed studies on cardiac conductance the was negative for QT prolongation for any of these doses. The subjects' heart rates increased maximally by 3.7 beats per minutes. Dose limiting toxicity was neutropenia at the 50 mg twice daily dose; with one of the 3 subjects having grade 4 neutropenia. A reversible increase in neutrophil counts was frequently seen at the higher doses tested and generally wore off within 24 hours of stopping treatment. The overall safety profile of ruxolitinib is good and the hematopoietic toxicities (i.e., thrombocytopenia, anemia and neutropenia) that were of greater concern in the Myelodysplastic Syndrome (MDS) patients with chronic treatment have not been observed in our ATL patients who received prolonged treatment previously as part of this protocol. This should not be that surprising with the genetic defect in MDS patients extending all the way down to their hematopoietic stem cells in contrast to the aberrant clone in ATL patients.⁴⁹

All patients who fulfill the Shimoyama Classification for smoldering or chronic or quiescent lymphomatous, or acute ATL, at the time of evaluation for entry into this study whether they have had prior treatment or not will be deemed eligible for this study. Patients will have their burden of circulating ATL cells assessed by serial FACS analysis of their PBMCs and when appropriate have their soft tissue disease formally assessed by the (cutaneous lesions) Dermatology Service or by CT scans of their known sites of disease. New patients will begin treatment at 30 mg orally twice daily. Despite the modest clinical experience with augmented dosing in NHVs, the long-term tolerability in ATL patients will have to be established with standard phase I dose escalation plan. If the first 3 patients treated at this dose level, do not have dose limiting toxicities dosing will proceed sequentially to 40 and, then, 50 mg twice daily in a standard 3+3 fashion. A total of 9 patients will be treated at the MTD or maximum administered dose (MAD) to better evaluate the clinical activity of the augmented dosing regimen.

Patients with a transient response to previous treatment at the standard 20 mg twice daily dose and

later progressed but otherwise meet the eligibility criteria on treatment will also be eligible to restart treatment.

1.7 RATIONALE FOR MULTIPLE ASSESSMENTS OF STAT5 AND PHOSPHOSTAT5

1.7.1 Cycle 1 day 1

Additional analysis *in vitro* of inhibition of proliferation in ATL cells obtained from patients with JAK inhibitors and results of the first patients treated in this trial suggest transient inhibition of JAK signaling in the patients' malignant cells may be occurring, but is not sustained due to our inability to maintain ruxolitinib serum levels above the 1 micromolar concentration required to inhibit signaling through JAK1. To investigate this hypothesis, we will be performing serial intracellular FACS analysis of STAT5 and phosphoSTAT5 and coordinate measurement of serum ruxolitinib levels on Cycle 1 Day 1 to more accurately characterize changes in STAT5 occurring after ruxolitinib treatment. Results from these analyses may provide preliminary *in vivo* information that will allow the next iteration of this treatment strategy to be analyzed in a more advanced manner.

1.7.2 Cycle 2 and later time points

Rather than have a fixed schedule of STAT5 and phosphoSTAT5 of assessments based on hypotheses, we have chosen to make the correlative immunologic and molecular correlative laboratory assessments at these later time points optional and determined by clinically important events. The plan will be to assess several patients treated with prolonged administration of Ruxolitinib at the time of their clinical safety evaluations to detect changes in the JAK-STAT signaling pathway. If a provocative signal is detected at a particular time point, continued testing of all patients being treated on a regular basis will be instituted.

2 ELIGIBILITY ASSESSMENT AND ENROLLMENT

2.1 ELIGIBILITY CRITERIA

2.1.1 Inclusion Criteria

NOTE: After approval and activation of Amendment D, patients who have failed this protocol treatment previously at the initial dose level may be eligible for re-enrollment and retreatment if they otherwise meet eligibility criteria.

- 2.1.1.1 Patients \geq 18 years old with pathologically confirmed adult T- cell leukemia: smoldering or chronic, or previously treated lymphomatous or acute subtypes with clinically indolent behavior indicated by lack of significant symptoms and treatment free interval of greater than 6 months are eligible for treatment in the dose escalation and expansion cohorts (see also [APPENDIX B](#)).
- 2.1.1.2 Patients must have serum antibodies directed to HTLV-1.
- 2.1.1.3 Patients must have measurable or evaluable disease. Patients with $> 10\%$ of the PBMCs having the characteristic abnormal (i.e., $CD3^{\text{dim}}$, $CD4^+$ $CD25^+$ expressing) FACS profile for circulating ATL cells will be considered to have evaluable disease.
- 2.1.1.4 Patients must have adequate physiologic parameters:
 - Absolute granulocyte count \geq 500 K/uL, platelet count \geq 75,000 K/uL and hemoglobin \geq 10 g/dL.
 - Bilirubin and creatinine \leq 1.5 x institutional ULN.
 - AST, ALT \leq 3.0 x institutional ULN.
- 2.1.1.5 Karnofsky Performance Score \geq 70% or ECOG \leq 1 ([APPENDIX A](#)).
- 2.1.1.6 Patients must be able to understand and sign Informed Consent Form.

2.1.2 Exclusion Criteria

- 2.1.2.1 Patients with symptomatic leukemic meningitis, bony or GI tract involvement, serum calcium or LDH > 1.5 X the upper limit of normal will be excluded. However, patients that have both ATL and another HTLV-1 associated disease such as tropical spastic paraparesis (HAM/TSP) will be included.
- 2.1.2.2 Patients with symptomatic leukemic meningitis, bony or GI tract involvement, serum calcium or LDH > 1.5 X the upper limit of normal will be excluded. However, patients that have both ATL and another HTLV-1 associated disease such as tropical spastic paraparesis (HAM/TSP) will be included.
- 2.1.2.3 Patients who have received high doses of systemic corticosteroids for the treatment of their ATL within 4 weeks prior to the start of therapy.
- 2.1.2.4 Patients who have received any cytotoxic therapy, immunotherapy, antitumor vaccines or monoclonal antibodies in the 4 weeks prior to the start of the study.
- 2.1.2.5 Life expectancy of less than 3 months.
- 2.1.2.6 Documented active bacterial infections, HTLV-II infection, or hepatitis B or C as

follows:

- A positive hepatitis B serology indicative of previous immunization (i.e., HBsAb positive and HBC Ab negative), or a fully resolved acute hepatitis B infection is not an exclusion criterion.
- Patients with an indolent chronic hepatitis B infection (normal ALT, AST, albumin and no radiographic or biopsy evidence of cirrhosis) may be eligible.
- Patients with active hepatitis C are excluded. Patients positive for hepatitis C virus (HCV) antibody are eligible only if polymerase chain reaction (PCR) is negative for HCV RNA.

2.1.2.7 Patients who have untreated human immunodeficiency virus (HIV) are not eligible for this study because by definition they have a defective immune response and are at much higher risk for opportunistic infections due to immune dysregulation by both HTLV-1 and HTLV-III (HIV) viruses. Patients on HIV therapy with undetectable viral loads as measured by HIV RNA quantitative real time PCR may be eligible.

2.1.2.8 Inability or refusal to practice effective contraception during therapy. Men and women of childbearing potential must use an effective method of birth control or abstinence during treatment and for 1 week after completion of the treatment.

2.1.2.9 Patient has significant and/or uncontrolled cardiac, renal, hepatic or other systemic disorders or significant psychological conditions at baseline visit that in the investigator's judgment would jeopardize subject enrollment or compliance with the study procedures.

2.1.2.10 Patients with an absolute requirement for a medication that is a strong inhibitor of P450 CYP3A4 (per **APPENDIX C**) are not eligible.

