1.6.3 Early Experience in this Trial

The initial 12 patients enrolled in the trial were treated with the standard 20 mg dose twice daily of off label ruxolitinib and tolerated the drug with little if any side effects, but responses were seen in only 4 of these patients. Three of these patients had more than a 50% decrease in the volume of their skin involvement and the other patient had 50% improvement in the number of circulating ATL cells, but the duration of these responses were 2 to 6 months. Serial analysis of phosphoSTAT 3 and phosphoSTAT5 on patients’ samples after treatment showed only transient inhibition of the phosphorylation of STAT 5 in the immediate post-treatment period. These results are consistent with the *ex vivo* inhibition experiments performed with ruxolitinib at the 1 and 10 μ M concentrations and ruxolitinib’s known pharmacokinetics (Cmax of 1.47 μ M \approx 2 hours post dose and terminal elimination $t_{1/2}$ of \approx 3 hours) resulting in a transient inhibition of the JAK-STAT signaling pathway that is marginally clinically active.

[figure not shown]
[figure not shown]

Figure 8: Effect of ruxolitinib on the endogenous phosphorylation of STAT3 and STAT 5 in ATL cells (ex vivo PBMCs isolated after oral ruxolitinib 20mg)

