on day 8. Patient who are tolerating their first 2 weeks of treatment well may be eligible to be monitored at home for the 3rd and 4th weeks of their cycle 1 treatment as stated in Section 3.1. Patients who have new complaints suggestive of toxicities will be seen as soon as possible for outpatient assessment of their condition. Patients who tolerate cycles 1 and 2 without any ≥ grade 2 toxicities or unanticipated adverse events, clinical monitoring visit maybe extended to every 2 cycles (i.e., 56 days) after cycle 4 once the tolerability of their treatment is established. For patients continuing treatment beyond 1 year, assessments may be extended to every 3rd or 4th cycle at the discretion of the investigator. The clinical and other research assessments may also be updated accordingly without being considered a protocol deviation

2. Denotes testing to be performed at the “end of study visit” (just prior to the patient being taken off study), if feasible.
3. Doses are 30, 40 and 50 mg twice daily.
4. Including biopsies of clinically suspicious skin lesions.
5. Vital signs include: weight, heart rate, blood pressure, respiration, temperature and arterial oxygen saturation (S_o2) by transcutaneous pulse oximeter, for follow up clinical evaluations.
6. Chemistry tests include acute care (sodium, potassium, chloride, CO₂, glucose, BUN, creatinine), mineral (serum calcium, phosphate, magnesium and albumin) and hepatic (alkaline phosphatase, ALT, AST, total and direct bilirubin) panels, LDH and CBC will be obtained twice weekly (e.g., M, Th) during the first week and then weekly during the first month of treatment with the higher doses. C-reactive protein(CRP) will at minimum be assessed day 1 of cycle 1, day 29 of cycles 2 and 4, and every 3-4 months in follow-up for all subsequent treatment cycles. These labs may also be performed at home by the patient’s referring physician when the patient is not seen in the outpatient clinic or if there is suspicion of clinical progression, if feasible.
7. Pretreatment day 1 or within 3 days prior to starting each cycle of treatment (ideally) when the patients are seen in follow-up at the Clinical Center in women of childbearing potential.

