3.8.2 Off-Study Criteria

- Completion of protocol therapy, with evidence of progression, including a 30-day safety visit
- Voluntary withdrawal of consent by the patient

- Patient non-compliance with treatment and research plans
- The institution of another anticancer treatment
- Any new medical or psychiatric condition that, in the opinion of the PI, precludes the safe continuation of the study
- Death

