6 DATA COLLECTION AND EVALUATION

6.1 DATA COLLECTION

The PI will be responsible for overseeing entry of data into an in-house password protected electronic system (C3D) and ensuring data accuracy, consistency and timeliness. The principal investigator, associate investigators/research nurses and/or a contracted data manager will assist with the data management efforts. All data obtained during the conduct of the protocol will be kept in secure network drives or in approved alternative sites that comply with NIH security standards. Primary and final analyzed data will have identifiers so that research data can be attributed to an individual human subject participant.

All adverse events, including clinically significant abnormal findings on laboratory evaluations, regardless of severity, will be followed until return to baseline or stabilization of event. AEs will be documented from the first study intervention, through 30 days following the last dose of study agent. Beyond 30 days after the last intervention, only adverse events which are serious and related to the study intervention need to be recorded

End of study procedures: Data will be stored according to HHS, FDA regulations, and NIH Intramural Records Retention Schedule as applicable.

Loss or destruction of data: Should we become aware that a major breach in our plan to protect subject confidentiality and trial data has occurred, this will be reported expeditiously per requirements in section [7.2.1](#).

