12.1.4 Caution

Women of child-bearing age and fertile men should be advised to use adequate and effective contraception during treatment with ruxolitinib and for at least six months after therapy. The effects of ruxolitinib on embryogenesis, reproduction, and spermatogenesis are unknown.

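### The binding contraception rule ends 1 week after treatment, while the protocol's own drug caution advises at least six months, and no visible text reconciles the two

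*Combined protocol and SAP*

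**What the plan says.** Two places in the protocol body give a contraception period after the last dose.

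- **Section 2.1.2.8 (Exclusion Criteria).** The criterion opens with "Inability or refusal to practice effective contraception during therapy". Its next sentence obliges men and women of childbearing potential to use an effective method of birth control or "abstinence during treatment and for 1 week after completion of the treatment".
- **Section 12.1.4 (Caution, in the pharmaceutical information).** Women of child-bearing age and fertile men should be advised to use contraception during treatment and "for at least six months after therapy". The section then states: "The effects of ruxolitinib on embryogenesis, reproduction, and spermatogenesis are unknown".

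Other sections deal with pregnancy but set no post-treatment contraception period. Section 10.1 excludes pregnant and breastfeeding women, citing the lack of significant preclinical information on fetal risk. Sections 2.2.11 and 2.4.8 call for serum pregnancy tests before treatment, and footnote 7 of the Study Calendar (section 3.5) ties later tests to the start of treatment cycles. Section 3.8.1 makes a positive test a reason to stop treatment.

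**The concern.** The same drug and, in substance, the same people are given two post-treatment periods of very different length. Staff working from the eligibility section would tell a patient 1 week; staff working from the drug section would say six months. Each could cite the protocol. The shorter period is the one that binds.

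What is at stake is reproductive safety in the months after stopping. The protocol itself treats that risk as open: section 12.1.4 calls the effects unknown, and section 10.1 gives missing fetal-risk information as its reason for excluding pregnant women. Having recorded that uncertainty, the protocol would be expected to carry its precaution into the rule that patients must follow, or to explain why it does not.

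The trial would also see little of what happens late in the gap. Section 6.1 says: "Beyond 30 days after the last intervention, only adverse events which are serious and related to the study intervention need to be recorded". Section 3.8.2 lists, among the reasons for leaving the study, "Completion of protocol therapy, with evidence of progression, including a 30-day safety visit". Patients who stop for another reason are followed until progression or another off-study reason (section 3.4.1.5), so the loss of sight is partial.

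**Working it through.** The plan gives no statistical figure to reproduce here. The check is a comparison of the two statements and a unit conversion.

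**Side by side**

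| | Section 2.1.2.8 | Section 12.1.4 |
|---|---|---|
| Who | Men and women of childbearing potential | Women of child-bearing age and fertile men |
| Force | Required | Advised |
| Period after treatment | 1 week | At least six months |
| Reason for the length | None given | None explicit; the next sentence says reproductive effects are unknown |
| Refers to the other section | No | No |

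**Can both be followed?** Yes. A patient who continues for six months has also met the 1-week rule. The reverse does not hold: meeting the 1-week rule does not meet the advice.

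**Size of the gap**

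- Six months = 365.25 / 2 = 182.6 days.
- Gap = 182.6 − 7 = 175.6 days, and 175.6 / 7 = 25.1 weeks.
- Ratio = 182.6 / 7 = about 26.

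**Does drug exposure explain six months?** Section 1.6.3 gives a terminal half-life of about 3 hours. One week is 7 × 24 / 3 = 56 half-lives. Residual drug is therefore not a reason for the longer period, and this figure favours the shorter one. What stays open is the reproductive effect that section 12.1.4 calls unknown.

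**How many people?** Section 8 sets the accrual ceiling at 35, of whom 12 were enrolled before Amendment D, so at most 35 − 12 = 23 enrolments fall under the amended design. This is a ceiling and not a count of people affected. Some of the 23 may be earlier patients re-enrolled under new numbers (section 2.3), some may already have finished treatment, and the documents do not give the fertile share.

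**The case against.** The strongest reply is that nothing here conflicts. An eligibility criterion sets an enforceable minimum, and a caution in the drug section adds longer precautionary counselling. Sites can enforce 1 week and counsel six months. The half-life supports a short requirement, and the other safeguards (exclusion of pregnant women, testing, stopping on a positive test) remain in place. On this view only a missing cross-reference is left.

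Much of that stands. It removes any claim of strict contradiction and keeps the point small. It does not show that the two-tier arrangement was intended, because the protocol never says so, and it leaves the binding rule well short of the protocol's own caution. The other safeguards operate before and during treatment and do not settle the period after it.

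Three stronger readings are tempting, and the documents do not support them.

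- **That six months is the correct period and 1 week is unsafe.** Neither section justifies its length, and the half-life points the other way.
- **That patients are being told the wrong thing.** The consent form is not in the public text, so what patients are told cannot be checked. The finding is limited to the protocol body.
- **That the opening clause of 2.1.2.8, which speaks only of refusal during therapy, leaves the post-treatment week outside eligibility.** This isolates one sentence. The next sentence makes the week obligatory, and the criterion reads naturally as a whole.

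**Conclusion.** The point holds as a minor inconsistency on patient safety. The protocol requires 1 week and advises at least six months, without reconciling them in any visible text. A patient who complies with the binding rule can stop about 25 weeks before the advised period ends.

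This rests on reading the two descriptions of who is covered as the same people in substance, and on six months being about 182.6 days. It does not rest on six months being pharmacologically necessary, which the documents do not show. No harm can be quantified, and the number of people affected is unknown. The toxicity rules, response rate, time to progression and sample size are untouched.

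**What to change.** Amend section 2.1.2.8 so that contraception is required during treatment and for at least six months after its completion, matching section 12.1.4, and check that the consent form says the same. This satisfies both sections and follows the protocol's own precaution. Adding only a cross-reference would tidy the text but leave the binding rule at 1 week. Cutting section 12.1.4 to 1 week would relax a precaution while reproductive effects are still described as unknown.

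**Cost.**

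- Fertile patients take on about 25 more weeks of required contraception.
- Part of that lies beyond follow-up. For a patient who leaves the study at the visit about 30 days after the last dose, 182.6 − 30 = 152.6 days (21.8 weeks) of the requirement would run after participation ends and could not be monitored.
- The Statement of Compliance requires IRB approval of the amendment and of any consent-form change, with a determination on whether existing participants must consent again.

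No statistical element of the plan needs to change.

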2.1.3 Recruitment Strategies

Patient accrual will be facilitated by the large number of clinical investigators who refer patients to the NCI and CCR. Contact letters or emails will be sent to the regional University referral center's Medical Oncologists informing them of this trial. In addition, this protocol may be abstracted into a plain language announcement posted on NIH websites and on NIH social media platforms.

2.2 SCREENING EVALUATION

2.2.1 Screening activities performed prior to obtaining informed consent

Minimal risk activities that may be performed before the subject has signed a consent include the following:

- Email, written, in person or telephone communications with prospective subjects
- Review of existing medical records to include H&P, laboratory studies, etc.
- Review of existing MRI, x-ray, or CT images
- Review of existing photographs or videos
- Review of existing pathology specimens/reports from a specimen obtained for diagnostic purposes

A waiver of consent for these activities has been requested in section **10.5.2**

2.2.2 Screening activities performed after a consent for screening has been signed

The following activities will be performed only after the subject has signed the study consent OR the consent for study 01-C-0129 (Eligibility Screening and Tissue Procurement for the NIH Intramural Research Program Clinical Protocols) (provided the procedure is permitted on that study) on which screening activities may also be performed. Assessments performed at outside facilities or on another NIH protocol within the timeframes below may also be used to determine eligibility once a patient has signed the consent.

Screening evaluation must be documented or performed within 28 days prior to initiating treatment:

2.2.3 Baseline history with documentation of sites of disease, physical examination, eligibility laboratory assessments. **NOTE:** For patients with skin lesions or other visually-apparent signs of disease, photographs may be taken to document and follow disease with permission.

